**Figure 2: The Hierarchical Test Order and Related Alpha Values**

The overall alpha error rate is controlled at the 0.05 level by following the above testing sequence and procedures.

Other secondary efficacy endpoints (number of transfusions, health-related QOL, and duration of CR) will be used as supportive evidence of the beneficial treatment effect, without formal hypothesis testing. Point estimates and 95% CIs will be obtained for the effect of treatment on these endpoints.

### 7.3.8 Number of RBC or Platelet Transfusions (Units)

One RBC transfusion is defined as 1 unit of RBC transfusion. Similarly, one platelet transfusion is defined as 1 unit of platelet transfusion. Dates and the number of RBC or platelet transfusions will be collected for each subject for a minimum 6 months (and until termination of study treatment if the study treatment lasts for more than 6 months), unless the subject dies or withdraws consent prior.

The total number of RBC or, separately, the total number of platelet transfusions up to the 6-month time point for each subject is counted from the date of randomization to Day 180, the date of last contact, or date of death, whichever occurs earlier. The number of transfusions up to Day 180 will be summarized using mean, standard deviation, median and quartiles. The 95% CI of the means will also be provided.

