- Slides should be Wright Giemsa or May Grunwald Giemsa stained. Send 1 or 2 PB and BM slides for each subject at each time point. Detailed instructions on collection, labeling and shipping are described in the Study Lab Manual. A BM sample adequate for analysis must be obtained. Repeat the BM sample if not interpretable.
- Response assessment is done on Day 1 of Cycles ≥ 2 based on BM aspirate/biopsy and the most concomitant PB. Assess PB at screening and on Day 1 of each cycle. Perform BM aspirate/biopsy at screening and then at the end of Cycles 2, 4, and 6 (ie, Day 1 of Cycles 3, 5, and 7 [± 7 -day window]) unless PB shows persistence of leukemic blasts that excludes the possibility of a marrow response. After blinded BM response is confirmed, assessment of normal count recovery is done based initially on the most concomitant PB counts and in later cycles on PB counts from Day 1 of each cycle to avoid transient treatment-induced normal count suppression. Subjects who discontinue treatment before Cycle 6 Day 1 before documented disease progression must undergo response assessment until disease progression or relapse is confirmed. After Cycle 6,

repeat BM aspirate/biopsy every 3 months for the first year on study and then every 6 months thereafter until PB or BM assessment shows disease progression or relapse. Refer to Section 9.2.

- q. **Hospitalizations/Transfusions:** Document all blood and platelet transfusions (blood product transfused and units) within 28 days before starting study treatment. Document all hospital admission and discharge dates and main reason for hospitalization, as well as all blood and platelet transfusions (blood product transfused and units), from Cycle 1 Day 1 and then monthly to 6 months after the first dose or to the Tx Dsc Safety FU visit, whichever is later. Not required for visits every 3 months in long-term follow-up.
- r. **Disease progression status:** For subjects who discontinue study treatment before disease progression is documented, PB and BM aspirate/biopsy assessments as described in footnote “p” should continue until disease progression or relapse is confirmed.

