9.5.2 Screening and Baseline Procedures

After the investigator or sub-investigator confirms that a subject is eligible and willing to participate in the study, study center personnel will randomly assign the subject to study treatment according to the study procedures manual.

Within 14 days before randomization (unless otherwise specified), perform the following study procedures and tests:

- Written informed consent. The ICF must be signed and dated by the subjects before any study-specific samples are collected or study-specific procedures are initiated.
- Complete medical history, including demographics. Record disease history, including the date of initial diagnosis and list prior treatments and responses to these treatments. Document concurrent medical signs and symptoms to establish baseline conditions. Prior treatments for MDS or other hematologic disorder, CMML, and AML should be recorded.
- Investigator's confirmation of eligibility. Perform all necessary procedures and evaluations to document that the subject meets each eligibility criterion.
- Complete physical examination including weight and examination of body systems according to institutional standards.
- Vital signs include resting systolic/diastolic blood pressure, resting respiration rate, resting heart rate, and body temperature.
- ECOG performance status.
- Height measurement (for BSA calculation).
- All study-procedure-related AEs from the time of informed consent.
- Record concomitant medications within 14 days before randomization.
- Blood and urine sample collection for laboratory assessments. (See [Table 17](#))
- Serum or urine pregnancy test: for women of child-bearing potential only, collected within 7 days before starting study treatment. Results must be negative for the subject to be eligible for enrollment into the study.
- Blood sample collection for cytogenetics and molecular genetics, collected within 28 days before starting study treatment.
- BM aspirate or biopsy for baseline disease assessment, cytogenetics, and molecular genetics, collected within 28 days before starting study treatment.
- All blood and platelet transfusions (blood product transfused and units) within 28 days before starting study treatment.
- Study treatment randomization, after eligibility is confirmed. Randomize as close as possible to the first dose of study treatment (on Cycle 1 Day 1), within a maximum of 1 week from Cycle 1 Day 1.

Table 17: Clinical Laboratory Tests

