11.6.8 Number of Red Blood Cell (RBC) or Platelet Transfusions

One transfusion is defined as 1 unit of RBC or 1 unit of platelets. Dates and the number of RBC or platelet transfusions will be collected for each subject. The average number of RBC or separately platelet transfusions per month will be summarized by treatment group. In addition, the number of RBC or platelet transfusions will also be summarized as a per-patient-year rate for each treatment group. The RR of these 2 per-patient-year rates (SGI-110 versus TC) and the associated 95% CI will be provided.

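### The transfusion analysis uses neither the baseline units already collected nor the stratification factors, so its treatment-effect interval may be wider than it needs to be

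*SAP*

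**What the plan says.** The protocol makes pre-treatment transfusions a scheduled item. Footnote q to the schedule of events (9.5.1) reads "Document all blood and platelet transfusions (blood product transfused and units) within 28 days before starting study treatment", and the screening list in 9.5.2 repeats it.

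SAP 7.3.8 defines the outcome as the number of units per subject, separately for RBC and platelets. The total "is counted from the date of randomization to Day 180, the date of last contact, or date of death, whichever occurs earlier". The analysis is: "The number of transfusions up to Day 180 will be summarized using mean, standard deviation, median and quartiles". It then adds: "The 95% CI of the means will also be provided". No between-arm estimator, covariate or stratification is named there.

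SAP 7.3.7, below Figure 2, says that transfusions and the other remaining secondary endpoints "will be used as supportive evidence of the beneficial treatment effect, without formal hypothesis testing". It continues: "Point estimates and 95% CIs will be obtained for the effect of treatment on these endpoints".

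Protocol 11.6.8 does name a between-arm estimate, a crude ratio of rates: "The RR of these 2 per-patient-year rates (SGI-110 versus TC) and the associated 95% CI will be provided". It has no baseline term and no strata, and SAP 7.3.8 does not carry it over.

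Elsewhere the SAP does adjust. The NDAOH model (7.3.5) includes the randomization factors, and the EQ-5D-5L model (7.3.9) includes the baseline value.

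**The concern.** Units given in the month before treatment are a direct baseline measurement of this endpoint. Subjects who arrive needing frequent transfusion can be expected to receive more units in either arm, so part of the between-subject variation in the outcome is probably predictable at randomization. SAP 3.1 describes the stratification factors as important for prognosis, and they may explain some more.

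A point estimate and confidence interval are the only inferential output promised for this endpoint. If predictable variation is left in, that interval is wider than the collected data require. No use of the baseline units is specified in either document.

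**Working it through.** **1. Inputs.** There are 400 subjects per arm (SAP 4.0). The documents give no SD, precision or power for transfusions, so there is no stated figure for this endpoint to reproduce. As a check on the N and allocation, I reproduced the plan's CR power (0.20 versus 0.30, two-sided alpha 0.04, 400 per arm). The null SE is sqrt(2 × 0.25 × 0.75 / 400) = 0.03062 and the alternative SE is sqrt((0.16 + 0.21) / 400) = 0.03041. Power = Φ((0.10 − 2.054 × 0.03062) / 0.03041) = Φ(1.22) = 0.889, against the stated 89%.

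**2. Unadjusted precision.** In outcome SD units, the 95% CI half-width for a difference in means is 1.96 × sqrt(2/400) = 0.139 SD.

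**3. Effect of baseline adjustment.** Let rho be the correlation between baseline units and units to Day 180. In a linear model the variance of the treatment difference is multiplied by 1 − rho², the CI width by sqrt(1 − rho²), and the equivalent sample size is 800 / (1 − rho²). The documents do not give rho, so the range below is an assumption.

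| rho | 1 − rho² | CI width ratio | Narrower by | Half-width (SD) | Equivalent N |
|---|---|---|---|---|---|
| 0.2 | 0.96 | 0.980 | 2.0% | 0.136 | 833 |
| 0.3 | 0.91 | 0.954 | 4.6% | 0.132 | 879 |
| 0.4 | 0.84 | 0.917 | 8.3% | 0.127 | 952 |
| 0.5 | 0.75 | 0.866 | 13.4% | 0.120 | 1067 |
| 0.6 | 0.64 | 0.800 | 20.0% | 0.111 | 1250 |

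**4. Adding the stratification factors.** If they explain a further 2% to 10% of the variance (also assumed), the width ratio at rho 0.3 is sqrt(1 − 0.09 − 0.02) = 0.943 to sqrt(1 − 0.09 − 0.10) = 0.900. At rho 0.5 it is 0.854 to 0.806. As main effects the factors cost 1 + 1 + 2 + 1 = 5 parameters.

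**5. Does the gain survive counts and deaths?** The linear formula is an approximation, because the outcome is a count that stops at death. A simulation used 400 trials per setting, 800 subjects, overdispersed counts, exponential survival with the plan's medians of 7 and 9 months, and robust standard errors. The transfusion rates and an effect of 0.85 were assumed, and strata were not modelled.

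| Observed correlation | SE ratio, mean difference | SE ratio, log rate ratio (Poisson, days-at-risk offset) |
|---|---|---|
| 0.15 | 0.99 | 0.99 |
| 0.40 | 0.91 | 0.90 |
| 0.59 | 0.80 | 0.76 |

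These agree with the approximation: almost nothing is gained below a correlation of about 0.2, and a useful amount from about 0.4.

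**The case against.** The strongest reply is that little depends on this. The endpoint is outside the alpha hierarchy and is not tested. The unadjusted comparison is valid under randomization, and leaving out the strata makes the interval conservative rather than biased. All of that stands.

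A reader might infer a loss of power. For a 0.2 SD difference, power would be Φ(0.2/0.0707 − 1.96) = 0.807 unadjusted, and 0.843 or 0.904 at rho 0.3 or 0.5. The documents plan no such test, so these figures describe nothing in the trial.

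A reader might also infer that chance baseline imbalance would distort the result. With 400 per arm the SE of a baseline difference is sqrt(2/400) = 0.07 SD. At rho 0.3 to 0.5 that moves the outcome difference by 0.02 to 0.035 SD, against a half-width of 0.139 SD that already allows for it.

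It would be too strong to say that the baseline units are used nowhere. The baseline list in SAP 7.2 is open-ended and would permit a table row, although it does not commit to one.

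The correlation is unknown and deaths may weaken it. With exponential survival at the plan's medians, 1 − 2^(−6/7) = 45% and 1 − 2^(−6/9) = 37% die by six months, so survival time drives part of the count. The comparison with other endpoints is only partial too: NDAOH is formally tested, and the EQ-5D-5L model has a baseline term but no strata.

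Finally, an estimator has to be named before it can be adjusted. Counting stops at death or last contact, so an arm with more early deaths shows fewer raw units. This is a fair point and it shapes the fix.

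**Conclusion.** The point holds as an inexpensive improvement of modest importance. A direct baseline of the endpoint is collected, a treatment-effect estimate with a 95% CI is promised, and no specified analysis uses that baseline or the stratification factors. The consequence is an interval wider than necessary on a supportive endpoint. The documents do not support reading it as bias, as inflated type I error, or as lost power for a claim.

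The size rests on the unknown correlation: about 2%, 5% and 13% narrower at rho 0.2, 0.3 and 0.5 by the linear approximation, and negligible below about 0.2. Any contribution from the strata is a further assumption.

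**What to change.** In SAP 7.3.8, for RBC and platelets separately, estimate the guadecitabine-versus-TC rate ratio and 95% CI from a negative binomial (or robust Poisson) model of units to Day 180. Include:

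- treatment;
- baseline units of the same product, for example log(1 + units);
- the four stratification factors, collapsed as in SAP 7.3.12 if needed;
- log days at risk as offset, where days at risk run from randomization to the earliest of Day 180, last contact and death.

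Report this beside the planned summaries. The offset keeps the estimate close in form to the protocol's per-patient-year ratio and accounts for unequal follow-up.

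Count baseline units only up to randomization. Outcome counting starts there, up to a week before the first dose, so a window ending at first dose would overlap the outcome. For dosed subjects this leaves 21 to 28 days of baseline. For subjects never dosed, anchor the 28 days at randomization.

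The split needs transfusion dates. Footnote q lists product and units for the baseline window but does not explicitly list dates, so confirm that they are captured. Add baseline units to the SAP 7.2 table.

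The cost is SAP wording, one model per product and one addition to the baseline table, with no new data if the dates are there. Because the sponsor is not blinded, the model should be fixed before outcomes are compared by arm.

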### 7.3.9 EQ-5D-5L Descriptive System Total Score and the EQ VAS

The EQ-5D-5L descriptive system scores and the EQ VAS will be collected for each subject for a minimum 6 months unless the subject dies or withdraws consent prior. The calculation for EQ-5D-5L index value will be performed according to EuroQol group's EQ-5D-5L User Guide (<http://www.euroqol.org/about-eq-5d.html>).

As suggested in the EQ-5D-5L User Guide (<http://www.euroqol.org/about-eq-5d.html>), the EQ-5D-5L descriptive scores and their dichotomized levels (No problems, Problems) within each EQ-5D dimension (mobility, self-care, usual activity, pain/discomfort, anxiety/depression), during the first 6 months, will be summarized by time (ie, visit/treatment cycle) descriptively, using counts and proportions. The EQ-5D-5L index value and VAS and their respective changes from baseline during the first 6 months will be summarized by time (ie, visit/treatment cycle) using means, standard deviations, medians and quartiles.

In addition, the changes from baseline (post baseline value - baseline value) of EQ-5D-5L index value, and separately EQ VAS, will be analyzed using a mixed model approach for repeated measures. This model will include the following terms as fixed effects: baseline value, treatment, time, and treatment-by-time interaction. The unstructured covariance matrix will be used to account for the within subject correlation and allow for different variances at different measurement times. The difference of the least squares means between the two treatment groups at each time (ie, visit/treatment cycle) and its corresponding 95% CI will be provided.

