11.6.9 EQ-5D-5L

The calculation for EQ-5D-5L (EQ-5D-5L descriptive system and EQ VAS; Appendix 4) scores (health profile, self-rated health status, and index value) will be performed according to EuroQol group (<http://www.euroqol.org/about-eq-5d.html>; 2009). Change from baseline in EQ-5D-5L scores will be summarized by visit. A repeated measures analysis of variance model will be used to compare the groups for change from baseline in EQ-5D-5L scores.

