## 3.0 STUDY DESIGN

### 3.1 Overall Study Design

This is a phase 3, multicenter, randomized, open-label study of guadecitabine versus TC. Blinded central reading of marrow and disease response will be performed. Subjects will be adults with previously untreated AML who are unfit to receive and not candidates for intensive remission induction chemotherapy.

Approximately 800 subjects from approximately 100-160 study centers will be randomly assigned (1:1) to 1 of 2 groups:

- Guadecitabine: 60 mg/m^2 guadecitabine given SC daily for 5 days (Days 1-5, Daily×5) in 28-day cycles.
- TC: subjects will be assigned (before randomization) by the investigator to 1 of the following treatment regimens:
  - 20 mg cytarabine (Ara-C) given SC BID on Days 1-10 every 28 days.
  - 20 mg/m^2 decitabine (Dacogen) given IV on Days 1-5 every 28 days.
  - 75 mg/m^2 azacitidine (Vidaza) given IV or SC on Days 1-7 every 28 days.

The randomization will have a ratio of 1:1 between guadecitabine and TC groups, and will be stratified by age (<75 or ≥75 years old), ECOG performance status (0-1, 2-3), study center region (North America, Europe, rest of world [ROW]), and secondary AML or poor-risk cytogenetics (Yes, No/Unknown). Subjects who are older (≥75 years) or have a poor performance status (2 or 3) tend to have worse response and survival than younger (<75 years) subjects or subjects with a good performance status (0 or 1). Similarly, subjects with a secondary AML or poor-risk cytogenetics generally do not respond to treatment well and have a shorter survival time. In addition, prognosis could have regional differences due to multiple factors including variable levels of Standard of Care. Stratification by these known and important prognostic factors measured at baseline prevents imbalance between treatment groups within strata, and could reduce bias and improve power of the study.

Selection of 1 of the TCs must be made prior to the randomization of each subject. Subjects should receive study treatment as soon as possible after randomization (maximum of 1 week between randomization and treatment).

The sponsor, investigators and study subjects are not blinded in this study. However, to minimize the potential bias associated with assessment of treatment outcome, response will be determined

[figure not shown]

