#### 7.3.5 Number of Days Alive and Out of the Hospital

The date of each hospital admission and discharge will be collected for each subject for a minimum 6 months (and until termination of study treatment if the study treatment lasts for more than 6 months), unless the subject dies or withdraws consent prior. The duration of each hospital stay in days (regardless of the reason for hospitalization) is calculated as:

$$\text{Duration} = \text{date of discharge} - \text{date of admission}$$

For a subject who is admitted and discharged on the same day the duration of hospital stay will be 0. The total duration of all hospital stays in the first 6 months is the sum of all individual

durations of hospital stays occurred between C1D1 and Day 180. For ease of calculation, one month is defined as 30 days for analyses conducted in this study. The NDAOH within the first 6 month period is calculated as:

$$\text{NDAOH} = 180 - \text{total duration of all hospital stays} - \text{number of death days before Day 180}$$

The number of death days before Day 180 = (date of Day 180 - date of death, if death occurs before Day 180). For subjects who die on or after Day 180 the number of death days before Day 180 will be set to 0. For subjects who are lost to follow-up within 6 months (expected to be a very small number), the NDAOH will be calculated conservatively assuming that the subject would have died the day after the last contact day.

The NDAOH will be summarized by treatment group and compared between the 2 treatment groups using an analysis of variance model at an alpha level of 0.05 or 0.01 as appropriate, if the CRc test result is significant at that required level (see Section 7.3.7). The variables used for stratification at randomization will be included in the analysis of variance model as fixed factors.

In addition, to utilize the information on hospital stays beyond 6 months, the NDAOH will also be calculated in a similar way to 6 months or the date of treatment discontinuation (whichever occurs later) and summarized as a per patient-year rate for each treatment group.

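### The EQ-5D index and EQ VAS models omit the four randomization stratification factors, so their reported 95% CIs may be modestly wider than the design warrants

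*SAP*

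**What the plan says.** SAP 7.3.9 specifies the model for change from baseline in EQ-5D-5L index, and separately in EQ VAS: "This model will include the following terms as fixed effects: baseline value, treatment, time, and treatment-by-time interaction". On the covariance it says: "The unstructured covariance matrix will be used to account for the within subject correlation". The reported result is the contrast by visit; the sentence that sets it out begins: "The difference of the least squares means between the two treatment groups at each time (ie, visit/treatment cycle) and its corresponding 95% CI will be". No other section adds a covariate to this model. Protocol 11.6.9 names none either: "A repeated measures analysis of variance model will be used to compare the groups for change from baseline in EQ-5D-5L scores".

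SAP 3.1 stratifies randomization by age (two levels), ECOG status (two), region (three) and secondary AML or poor-risk cytogenetics (two). Its reason is: "Stratification by these known and important prognostic factors measured at baseline prevents imbalance between treatment groups within strata, and could reduce bias and improve power". The outcomes it has in mind are response and survival; of older subjects or those with poor performance status it says that they "tend to have worse response and survival than younger (<75 years) subjects" or those with good performance status.

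For the other continuous endpoint, days alive and out of the hospital (NDAOH), SAP 7.3.5 says: "The variables used for stratification at randomization will be included in the analysis of variance model as fixed factors". SAP 7.3.7 classes quality of life, transfusions and duration of CR as supportive. They have no formal test and are reported as point estimates with 95% CIs.

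**The concern.** When randomization is stratified, a model-based standard error that ignores the strata counts between-stratum variation as noise, although the design has already removed it from the treatment comparison. If the factors predict the outcome, the reported interval is then too wide for the design.

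The SAP avoids this for NDAOH. Protocol 11.6.5 planned a two-sample t-test, which the SAP replaced with an analysis of variance containing the factors. The SAP also rewrote the protocol's EQ-5D model, but did not add the factors and gives no reason. EQ-5D is the trial's only patient-reported endpoint and has no formal test, so the interval at each visit is its whole inferential output.

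**Working it through.** **The plan's own figures.** The documents give no SD, effect size or precision target for EQ-5D, so there is no EQ-5D figure to reproduce. The trial sizing in SAP 4.0 reproduces:

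- CR, 400 per group, 0.20 v 0.30, two-sided alpha 0.04: Φ[(0.10·√400 − 2.054·√(2·0.25·0.75)) / √(0.20·0.80 + 0.30·0.70)] = Φ(1.22) = 0.889, against a stated 89%.
- OS, 670 deaths: Φ(|ln HR|·√(670/4) − 1.96) = 0.895 at HR 0.78 and 0.902 at HR 7/9, against a stated 90%.

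Neither depends on the EQ-5D model.

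**Effect on the reported interval.** Let R² be the share of residual variance, after baseline EQ-5D, that the four factors explain. It is an assumption throughout. In large samples the ratio of CI widths, with the factors to without, is √(1 − R²). As main effects the factors cost 1 + 1 + 2 + 1 = 5 parameters. At one visit with n scores, and three parameters already fitted (intercept, treatment, baseline), the ratio becomes √[(1 − R²)(n − 3)/(n − 8)].

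| Assumed R² | CI change, large sample | CI change with 5-parameter cost, n = 800 |
|---|---|---|
| 0% | none | 0.3% wider |
| 2% | 1.0% narrower | 0.7% narrower |
| 5% | 2.5% narrower | 2.2% narrower |
| 10% | 5.1% narrower | 4.8% narrower |
| 20% | 10.6% narrower | 10.3% narrower |

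Fewer scores change little. At n = 400 the results are 0.6% wider at R² = 0 and 4.5% narrower at R² = 10%.

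**Does the estimate itself become less variable?** This was simulated with stratified block randomization over the 24 strata (2 × 2 × 3 × 2), one visit, complete data, n = 600, 3,000 replicates, and baseline in both models.

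| Assumed R² | Reported SE, without factors | Reported SE, with factors | True sampling SD, without | True sampling SD, with |
|---|---|---|---|---|
| 2% | 0.0817 | 0.0809 | 0.0793 | 0.0793 |
| 5% | 0.0817 | 0.0797 | 0.0798 | 0.0798 |
| 10% | 0.0818 | 0.0776 | 0.0766 | 0.0766 |
| 20% | 0.0818 | 0.0731 | 0.0735 | 0.0733 |

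The true sampling SD is almost the same in both models; only the reported SE differs. At R² = 10% the Monte Carlo error of the SD is about 0.0766/√(2 × 3,000) = 0.0010. The adjusted SE agrees with the true SD within that error, while the unadjusted SE exceeds it by 0.0052.

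**What this does to coverage.** At R² = 10% the unadjusted nominal 95% interval covers about 2Φ(1.96/0.9487) − 1 = 2Φ(2.066) − 1 = 96.1%, so the error is conservative.

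**The case against.** The strongest reply is that the SAP follows a pattern. The five endpoints in the testing hierarchy (CR, OS, CRc, NDAOH, PFS) use the factors, and the supportive ones do not: transfusions (SAP 7.3.8) and duration of CR (7.3.10) are also unstratified. On that view adding the factors to EQ-5D is a preference, with little gain on a supportive endpoint. Much of this stands, including the limited consequence. But of the three supportive endpoints, EQ-5D is the only one for which the SAP specifies a between-group regression model. An interval from that model should reflect the way subjects were randomized.

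A second reply also stands. Nothing in the documents shows that the factors predict EQ-5D change once baseline score is in the model. The ECOG descriptions overlap in content with the EQ-5D mobility, self-care and usual-activities items, so baseline EQ-5D may already carry much of that information.

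The protocol synopsis and section 4.1 say that randomization and analyses are stratified by the four factors. A reader might infer a rule that SAP 7.3.9 breaks. The sentence follows the statement on the co-primary endpoints, and the same protocol gives NDAOH an unstratified t-test. It is too weak to establish a breach.

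**Conclusion.** The omission is real and minor. The EQ-5D intervals are conservative by an amount set by a residual R² that the documents do not give: about 1% to 5% of width at an assumed 2% to 10%, and nothing to gain at zero. The calculation treats one visit with complete data; missing scores after death or withdrawal were not modelled.

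Three stronger readings are tempting and are not supported:

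- **The treatment estimate is less precise than it could be.** Its true variability is practically the same with or without the factors, because the randomization balances them. The fault lies in the reported standard error.
- **The factors are strong predictors of EQ-5D.** SAP 3.1 links them to response and survival only.
- **Omitting them adds bias from dropout by death.** At the planning medians of 7 and 9 months, assuming exponential survival, 1 − 0.5^(6/7) = 45% and 1 − 0.5^(6/9) = 37% would be dead by month 6. Those figures count deaths; they do not measure what omitting the covariates does to the estimate. Baseline covariates also do not settle how a score after death should be treated, which is a separate question.

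**What to change.** In SAP 7.3.9, add age group, ECOG group, region and secondary AML or poor-risk cytogenetics, coded as at randomization, as fixed effects in both the EQ-5D index and the EQ VAS models. Extend the SAP 7.3.12 collapsing order to these models in case cells are sparse. If the sponsor prefers to leave the factors out, the SAP should say why and note that the intervals are then conservative to the extent that the factors are predictive.

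The cost is one sentence in the SAP, a change to the model statement and five parameters. All four factors are recorded at randomization, so no new data are needed. The downside is small: intervals about 0.3% wider at n = 800 if the factors explain nothing. Main effects also assume that each factor acts equally at every visit, so less is gained where that is not so.
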